**Table 1: Guidelines for Interruption and Restarting of Itacitinib/Placebo**

ADVERSE EVENT	ACTION TAKEN
Chemistry	

 
• AST and/or ALT > 3.0 × ULN in subjects with normal ALT/AST at baseline.
 
	
 
• Interrupt for up to 14 days until the toxicity has resolved to ≤ Grade 1. Exceptions require sponsor approval.
 
• Restart at previous dose. If assessed as related to itacitinib/placebo, restart at next lower dose and monitor as clinically indicated.
 
• NOTE: In subjects with GVHD-related chemistry elevations at baseline, contact the sponsor medical monitor to discuss clinical management and possible dose reductions.
 

 
• Total bilirubin elevations that occur in the presence of GVHD response that cannot be attributed to new liver GVHD or concomitant therapy.
 
	
Total bilirubin 3.0-5.0 × ULN:
 
 
• Repeat assessment within 7 days. If elevation persists: 
 
– Reduce dose by 1 level until bilirubin ≤ 1.5 × ULN.
 
– Resume previous dose if resolved in 14 days; if > 14 days, maintain reduced dose.
 
 
 
 
Total bilirubin > 5.0-10.0 × ULN:
 
 
• Repeat assessment within 7 days. If elevation persists: 
 
– Interrupt until bilirubin ≤ 1.5 × ULN.
 
– Monitor LFTs weekly or more frequently as appropriate.
 
– Resume previous dose if resolved in 14 days; if > 14 days, resume at reduced dose.
 
 
 
 
Total bilirubin > 10.0 × ULN:
 
 
• Repeat assessment within 7 days. If elevation persists: 
 
– Interrupt until bilirubin ≤ 1.5 × ULN.
 
– Resume at reduced dose if resolved in 14 days; if > 14 days, discontinue treatment and monitor as appropriate.
 
 
 


 
• Total bilirubin elevations that occur in subjects with Stage 1/2 liver GVHD that cannot be attributed to worsening liver GVHD or concomitant therapy.
 
	
Total bilirubin > 3.0 × ULN:
 
 
• Repeat assessment within 7 days. If elevation persists: 
 
– Reduce dose by 1 dose level.
 
– Resume previous dose if bilirubin ≤ 3.0 × ULN.
 
 
 

Hematology	

 
• ANC < 0.5 × 10^9/L, suspected as unrelated to study treatment (eg, GVHD, active cytomegalovirus viremia).
 
	
 
• Reduce dose by 1 dose level.
 
• Monitor ANC count as clinically indicated.
 
• Resume previous dose if ANC count is ≥ 0.5 × 10^9/L for more than 7 days.
 

 
• ANC < 0.5 × 10^9/L, suspected as related to study treatment.
 
	
 
• Interrupt for up to 14 days.
 
• Monitor ANC count as clinically indicated.
 
• Resume at a reduced dose if ANC count is ≥ 0.5 × 10^9/L for more than 7 days. If the subject's ANC count remains at ≥ 0.5 × 10^9/L for more than 7 days after resuming treatment at a lower dose, the previous dose may be resumed.
 

**Table 1: Guidelines for Interruption and Restarting of Itacitinib/Placebo (Continued)**

ADVERSE EVENT	ACTION TAKEN

 
Platelet count is <math>< 10 \times 10^9/L</math>, or platelet count has decreased by <math>\geq 50\%</math> from baseline, suspected as unrelated to study treatment.
 
	
 
Reduce dose by 1 dose level.
 
Monitor platelet count as clinically indicated.
 
Resume at previous dose if platelet count returns to <math>\geq 20 \times 10^9/L</math> or within 75% of baseline for more than 7 days.
 

 
Platelet count is <math>< 10 \times 10^9/L</math>, or platelet count has decreased by <math>\geq 50\%</math> from baseline, suspected as related to study treatment.
 
	
 
Interrupt for up to 14 days.
 
Monitor platelet count as clinically indicated.
 
Resume at a reduced dose if platelet count returns to <math>\geq 20 \times 10^9/L</math> or within 75% of baseline for more than 7 days. If the subject's platelet count remains stable for an additional 7 days, the previous dose of may be resumed.
 

Other toxicities	

 
Any Grade 1 or Grade 2 toxicity.
 
	
 
Continue treatment and manage the toxicity.
 
Monitor as clinically indicated.
 

 
Any Grade 3 toxicity, if clinically significant and not manageable by supportive care.
 
	
 
Interrupt up to 14 days until toxicity resolves to <math>\leq</math> Grade 1.
 
Restart at same dose; if assessed as related to itacitinib/placebo, restart at next lower dose and monitor as clinically indicated.
 

 
Any recurrent Grade 3 toxicity at 100 mg QD dose.
 
	
 
Discontinue study treatment; follow-up per Protocol. Exceptions require sponsor approval.
 

 
Any other Grade 4 toxicity.
 
	
 
Discontinue study treatment; follow-up per Protocol.
 

ALT = alanine aminotransferase; ANC = absolute neutrophil count; AST = aspartate aminotransferase; ULN = upper limit of normal.

**Table 2: Dose Reduction Levels for Itacitinib**

Current Dose	First Dose Reduction	Second Dose Reduction
200 mg QD	100 mg QD	Discontinue

### 5.4.3. Tapering of Itacitinib/Placebo

If a subject has achieved CR or VGPR at Day 180, investigators may begin to taper the dose of itacitinib/placebo by 1 dose level provided corticosteroids have been discontinued for at least 8 weeks following institutional guidelines. Subsequent tapering may occur within 28 to 56 days after the initial taper as appropriate.

Subjects who are still receiving calcineurin inhibitors or other agents for GVHD prophylaxis at this time may continue to do so at the treating investigator's discretion. In addition, subjects must not be experiencing any Grade 2 or higher hematologic toxicity related to study treatment or symptoms of an active infection.

Investigators wishing to initiate a taper of itacitinib/placebo at an earlier timepoint may do so upon consultation with and approval from the sponsor's medical monitor.

If GVHD signs/symptoms worsen during the taper of itacitinib/placebo, the dose may be escalated by 1 dose level. If the subject requires additional systemic therapy (includes restarting of corticosteroids), then the subject would be considered as having progression of disease and

would be withdrawn from study treatment. A physiologic dose of 6 to 8 mg/day of methylprednisolone (ie, 7.5-10 mg/day of prednisone) during itacitinib/placebo taper is allowed and will not be considered treatment failure.

If subjects completely taper off itacitinib/placebo and GVHD signs/symptoms reappear at a later time, subjects may enter the re-treatment phase at the investigator's discretion (Section 6.4). Assessments would be performed as per the re-treatment assessment schedule listed in Table 3.

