**Study Drug, Dosage, and Mode of Administration:**

Subjects will begin treatment with itacitinib or placebo at a dose level of 200 mg (2 × 100 mg tablets) taken by mouth (PO) QD. Subjects may have dose reductions and interruptions during the course of treatment based on safety and laboratory assessments. Tapering of itacitinib or placebo is permitted provided that the subject has reached the Day 180 visit, achieved a CR or VGPR, and discontinued corticosteroid therapy for at least 8 weeks. The dose of itacitinib or placebo may be escalated if GVHD flares during the course of a taper. Subjects who experience worsening GVHD during itacitinib or placebo dose escalation and require additional therapy will be considered as having progressive disease and be withdrawn from treatment.

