#### **5.2.3. Starting Dose and Administration of Corticosteroids**

All subjects will receive methylprednisolone 2 mg/kg IV daily (or prednisone equivalent) or at a dose that is appropriate for the severity of disease as outlined per local treatment guidelines ([Martin et al 2012](#), [Ruutu et al 2014](#)) as background treatment. Subjects who previously began corticosteroid therapy at a different dose may remain on that dose if considered clinically appropriate by the treating physician. Corticosteroids should be tapered as per institutional guidelines at a rate that is commensurate with resolution of GVHD manifestations.

If GVHD flares during the taper of prednisone or methylprednisolone, the dose may be re-escalated at the investigator's discretion and will not be considered treatment failure, as long as the dose does not exceed the initial starting dose. If the dose required exceeds this threshold, or if the flare is not responsive to increased corticosteroids or multiple flares are observed, then the subject will be considered to have experienced treatment failure and be withdrawn from study treatment.

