#### **5.5.1. Withdrawal Criteria**

Subjects **must** be withdrawn from study treatment for the following reasons:

- The subject has experienced an unacceptable toxicity.
- Relapse of underlying malignancy.
- The subject is unable to tolerate itacitinib/placebo at a dose of 100 mg QD.
- Additional systemic therapy is required for GVHD progression or lack of response, including corticosteroid doses greater than those used on Study Day 1.
- Further participation would be injurious to the subject's health or well-being, in the investigator's medical judgment.
- The subject becomes pregnant.
- Consent is withdrawn.

- The study is terminated by the sponsor.
- The study is terminated by the local health authority, IRB, or IEC.

A subject **may** be withdrawn from study treatment as follows:

- If, during the course of the study, a subject is found not to have met eligibility criteria, then the medical monitor, in collaboration with the investigator, will determine whether the subject should be withdrawn from the study.
- If a subject is noncompliant with study procedures or study drug administration in the investigator's opinion, the sponsor should be consulted for instruction on handling the subject.

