## **6.4. Re-Treatment**

For subjects who experience aGVHD recurrence after taper of randomized treatment is completed, investigators have the option to use open-label itacitinib plus corticosteroids for the treatment of recurrent aGVHD irrespective of initial randomized treatment. For the purpose of this Protocol, treatment of recurrent aGVHD with open-label itacitinib plus corticosteroids will be called the re-treatment phase. Subjects entering the re-treatment phase will be required to follow the assessment schedule as outlined in [Table 3](#). Corticosteroid tapering will be performed at the investigator's discretion. Investigators wishing to initiate a taper of itacitinib earlier than Day 180 may do so upon consultation with and approval from the sponsor's medical monitor. Subjects may be re-treated with itacitinib only once. Subjects ending the re-treatment phase will repeat the EOT visit and subsequent safety and survival follow-up visits.

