7.1. General Considerations

In all efficacy analyses, initiation of new, systemic anti-GVHD therapy includes 2 scenarios:

1) initiation of new anti-GVHD therapy including a higher dose of corticosteroid than that used at Day 1 and 2) initiation of new, systemic anti-GVHD therapy when subjects who were treated with placebo in the treatment phase were re-treated with itacitinib in the retreatment phase.

Initiation of new, systemic anti-GVHD therapy will be considered when defining the following:

1) onset of response and 2) loss of response. When defining responder for Day 28 ORR; overall response at Days 14, 56, 100, and 180; and BOR, the onset of response will be censored by initiation of new, systemic anti-GVHD therapy. Responders who did not have GVHD progression or death after response will be censored at the time of either study withdrawal, initiation of new, systemic anti-GVHD therapy, or the date of last assessment of GVHD before or on the cutoff date, whichever is earliest. In the survival analysis of NRM, all subjects in the analysis set in question without a death due to causes other than malignancy relapse will be censored at either study withdrawal, death due to malignancy relapse, or the date of last contact before or on the cutoff date, whichever is earliest.

Duration of response will be calculated for every subject who has a response in the study; DOR will also be summarized for any subgroups of interest.

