7.3.3. Alternative Ways of Calculating Duration of Response for Day 28 Responders

There are 2 other ways of calculating DOR for Day 28 responders:

- **DOR alternate approach 1** – DOR is defined as the interval from Day 28 to either death or initiation of new anti-GVHD therapy, including a higher corticosteroid dose than that administered at Day 1, whichever is earlier.
- **DOR alternate approach 2** – DOR is defined as the interval from Day 28 to the earliest of death, worsening from best response at or after Day 28 in any organ stage, or initiation of new anti-GVHD therapy (including a higher corticosteroid dose than that administered at Day 1).

Summary statistics and KM estimate will be provided by treatment group. Kaplan-Meier plots will also be provided.

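### SAP 7.1 and 7.3.3 name corticosteroids as new anti-GVHD therapy only above the Day 1 dose, so on the more natural reading alternate DOR approach 1 has no event at a lower-dose restart during the study-drug taper (minor)

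*Protocol*

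**What the plan says.** **Study-drug taper.** Protocol 5.4.3 opens the itacitinib/placebo taper at Day 180 for subjects in CR or VGPR who have been off corticosteroids for at least 8 weeks; an earlier start needs the medical monitor's approval. If GVHD worsens during the taper, "If the subject requires additional systemic therapy (includes restarting of corticosteroids), then the subject would be considered as having progression of disease", and the subject is withdrawn from study treatment. The one dose exemption is 6 to 8 mg/day of methylprednisolone. The synopsis is similar: "Subjects who experience worsening GVHD during itacitinib or placebo dose escalation and require additional therapy will be considered as having progressive disease".

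**Steroid taper and general withdrawal rule.** Under Protocol 5.2.3, re-escalating steroids for a flare during the steroid taper "will not be considered treatment failure, as long as the dose does not exceed the initial starting dose". Protocol 5.5.1 requires withdrawal when additional systemic therapy is needed, "including corticosteroid doses greater than those used on Study Day 1".

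**SAP definition.** SAP 7.1, written for all efficacy analyses, gives two scenarios for new systemic therapy. The first is "initiation of new anti-GVHD therapy including a higher dose of corticosteroid than that used at Day 1". The second arises "when subjects who were treated with placebo in the treatment phase were re-treated with itacitinib in the retreatment phase".

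**Endpoints that use it.**
- Approach 1 (SAP 7.3.3) runs from Day 28 to death or "initiation of new anti-GVHD therapy, including a higher corticosteroid dose than that administered at Day 1, whichever is earlier".
- Approach 2 adds worsening of any organ stage.
- Main DOR (SAP 7.3.2) ends at progression or death, and otherwise censors at new anti-GVHD therapy.
- FFS (SAP 7.4.9) is defined by, among other things, no need for further aGVHD treatment. Its event list carries no steroid threshold and omits the word *new*; its censoring sentence includes that word.

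**The concern.** The Day 1 threshold in the SAP fits the situations in Protocol 5.2.3 and 5.5.1. It does not fit the study-drug taper, where the subject is already off steroids and the protocol treats any above-physiologic restart as additional systemic therapy and progression. That special case was not carried into the SAP. SAP 10.1, which lists changes to protocol-defined analyses, does not mention it.

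At stake is whether a responder who flares mid-taper, restarts steroids and is withdrawn can still count as an ongoing response in one of the planned DOR summaries. The uneven use of *new* in the FFS section could also lead two programmers to build slightly different events.

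**Working it through.** **1. One case, followed through each rule.** A Day 28 responder reaches the taper, flares, and restarts steroids above 8 mg/day methylprednisolone but at or below the Day 1 dose.

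| Rule | Result at the restart |
|---|---|
| Protocol 5.4.3 | Additional systemic therapy, progression, withdrawal from study treatment |
| SAP 7.1, scenario 1 | Not named: dose is not above Day 1 |
| SAP 7.1, scenario 2 | Not met: not a placebo subject entering re-treatment |
| Approach 1 | No death and no named new therapy, so no event |
| Approach 2 | Event if an organ stage worsens |
| Main DOR | Event if progression is recorded |
| FFS | Event by the definition and event list; the censoring sentence is less clear |

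**2. Does *including* cover the restart anyway?** Scenario 2 suggests not. In Protocol 6.4, "investigators have the option to use open-label itacitinib plus corticosteroids for the treatment of recurrent aGVHD irrespective of initial randomized treatment". Both arms then receive steroids again, yet SAP 7.1 counts re-treatment as new therapy only for placebo subjects. If a steroid restart alone were new therapy, limiting scenario 2 to placebo would serve little purpose. The narrow reading is therefore the more natural one, though not the only one. On the broad reading a different gap opens: if progression is not recorded, main DOR would censor at the restart instead of counting an event.

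**3. Dose range affected (illustration, assumed 70 kg).** Protocol 5.4.3 acts above 8 mg/day. The SAP names steroids above 70 mg/day (Day 1 dose 1 mg/kg) or 140 mg/day (2 mg/kg). Ratios: 70/8 = 8.75 and 140/8 = 17.5.

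**4. One subject (illustration).** Restart on Day 200 at 1 mg/kg after a Day 1 dose of 2 mg/kg. Ending at the restart: 200 − 28 = 172 days. Followed to Day 365 with no later event: 365 − 28 = 337 days. Difference: 337 − 172 = 165 days. SAP 7.3.3 gives approach 1 no censoring rule of its own. If the subject were instead censored at the last GVHD grading, the time would not run on, but the failure would still go uncounted.

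**5. Effect of one missed event on the curve.** Approach 1 covers Day 28 responders. At the design rates with 218 per arm: 218 × 0.56 = 122 (placebo) and 218 × 0.72 = 157 (itacitinib). The Kaplan-Meier drop for one event is S(t)/n(t), with n(t) = N × S(t) × G, where G is the share not yet censored. The drop is therefore 1/(N × G).

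| G (assumed) | N = 122 | N = 157 |
|---|---|---|
| 1.0 | 0.82 points | 0.64 points |
| 0.7 | 1.17 points | 0.91 points |
| 0.5 | 1.64 points | 1.27 points |

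Some censoring is likely, because the final analysis is timed on the last subject's Day 180 visit.

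**6. Number of such events.** The documents give neither a taper rate nor a restart rate, so the total cannot be derived.

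**The case against.** The strongest reply is that *including* is illustrative. Protocol 5.5.1 uses almost the same phrase, and it fits with 5.4.3 only if it is not exhaustive. Starting steroids after 8 weeks without them can be read as initiating new therapy. The Day 1 clause keeps a purpose on that reading, since it catches escalation of steroids still being given. This stands as a possible reading. Scenario 2 still points the other way, although it concerns the period after a completed taper and so bears on the point only indirectly.

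Second, approach 1 leaves out progression by design, so passing over a progression is not in itself an error. That stands too. What remains is that the protocol also calls the restart additional systemic therapy, which is the kind of event approach 1 is meant to count.

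Third, other routes exist. The withdrawal reason goes into the eCRF (Protocol 5.5.2) and GVHD is graded at the EOT visit (7.6.1), so main DOR and approach 2 will usually register the failure. This largely stands. The limit is that Protocol 6.5.2 provides later GVHD follow-up only for subjects who stopped for other reasons, so what is missed by EOT is unlikely to be recovered.

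A reader might infer that FFS is equally exposed. The documents do not support that: its definition and its event list both favour counting the restart, and only the censoring sentence needs aligning.

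**Conclusion.** The mismatch is real and minor. On the more natural reading of SAP 7.1 and 7.3.3, approach 1 has no event at an above-physiologic steroid restart at or below the Day 1 dose during the study-drug taper. Approach 1 is a descriptive alternative, reported with summary statistics and Kaplan-Meier estimates.

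A reader might go on to infer that the main results are at risk. They are not. The taper normally opens at Day 180, well after the Day 28 response, and NRM counts deaths. Month 6 FFS could be touched only through early tapers approved by the medical monitor. No confirmatory test depends on this definition.

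Nor do the documents support a claim that the wording favours itacitinib: the steroid threshold is the same in both arms, and no restart rates by arm are given. The dose ratios and the 165 days are illustrations, not effects. The only size that can be stated is per event: 0.64 to 0.82 points without earlier censoring, and 1.27 to 1.64 if an assumed half are censored. Few subjects are likely to qualify, since each must be a Day 28 responder, normally in CR or VGPR at Day 180, off steroids for 8 weeks, and flare before the taper ends.

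**What to change.** Add to SAP 7.1, with cross-references in 7.3.2, 7.3.3 and 7.4.9:

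> A restart of systemic corticosteroids for GVHD above the Protocol 5.4.3 physiologic dose, from the first itacitinib/placebo taper step until the taper is completed (including a restart when study drug is stopped for that flare), counts from its start date as progression, an event and not censoring, for main DOR, and as initiation of new anti-GVHD therapy for FFS and alternate DOR approaches 1 and 2, whatever the Day 1 dose and identically in both arms.

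Align the FFS censoring sentence in SAP 7.4.9 with its event list. Leave re-treatment after a completed taper as it is. The protocol needs no change.

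The cost is one sentence, three cross-references and a programming rule. The data are already planned: SAP 6.5 tabulates tapered doses, the schedule of assessments includes steroid dose monitoring, and Listing 2.5.3 covers corticosteroid use after end of treatment. The downside is that DOR and FFS become slightly less favourable.

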#### **5.4.4. Criteria for Permanent Discontinuation of Study Drug**

The occurrence of unacceptable toxicity not caused by the underlying disease or malignancy will be presumed to be related to study drug treatment and will require that the study drug be permanently discontinued. Unacceptable toxicity is defined as follows:

- Occurrence of an AE that is related to treatment with the study drug that, in the judgment of the investigator or the sponsor's medical monitor, compromises the subject's ability to continue study-specific procedures or is considered to not be in the subject's best interest.
- Persistent AE requiring a delay of therapy for more than 14 days, unless a greater delay has been approved by the sponsor.

#### **5.4.5. Criteria and Procedures for Dose Interruptions or Adjustments of Corticosteroids**

Adjustments to the dose of corticosteroids should be made at the treating investigator's discretion.

### **5.5. Withdrawal of Subjects From Study Treatment**

The decision to discontinue study treatment will not constitute study completion (see Section 5.5.3). In the event that the decision is made to discontinue study treatment, the treatment period will be considered complete, and the follow-up period will begin.

#### **5.5.1. Withdrawal Criteria**

Subjects **must** be withdrawn from study treatment for the following reasons:

- The subject has experienced an unacceptable toxicity.
- Relapse of underlying malignancy.
- The subject is unable to tolerate itacitinib/placebo at a dose of 100 mg QD.
- Additional systemic therapy is required for GVHD progression or lack of response, including corticosteroid doses greater than those used on Study Day 1.
- Further participation would be injurious to the subject's health or well-being, in the investigator's medical judgment.
- The subject becomes pregnant.
- Consent is withdrawn.

- The study is terminated by the sponsor.
- The study is terminated by the local health authority, IRB, or IEC.

A subject **may** be withdrawn from study treatment as follows:

- If, during the course of the study, a subject is found not to have met eligibility criteria, then the medical monitor, in collaboration with the investigator, will determine whether the subject should be withdrawn from the study.
- If a subject is noncompliant with study procedures or study drug administration in the investigator's opinion, the sponsor should be consulted for instruction on handling the subject.

